## 9. Study Assessments and Procedures

Section 2 lists the Schedule of Activities, detailing the study procedures and their timing (including tolerance limits for timing).

[Appendix 2](#) lists the laboratory tests that will be performed for this study.

[Appendix 5](#) provides a summary of the approximate number and volume of invasive samples, for all sampling, during the study.

The specifications in this protocol for the timings of safety and sample collections are given as targets to be achieved within reasonable limits. Modifications may be made to the time points based upon emerging clinical information. The scheduled time points may be subject to minor alterations; however, the actual time must be recorded correctly in the eCRF. Failure or delays (ie, outside stipulated time allowances) in performing procedures or obtaining samples due to legitimate clinical issues (eg, equipment technical problems, venous access difficulty, or subject defaulting or turning up late on an agreed scheduled procedure) will not be considered as protocol deviations but the CRU will still be required to notify the sponsor in writing via a file note.

Unless otherwise stated in subsections below, all samples collected for specified laboratory tests will be destroyed within 60 days of receipt of confirmed test results. Certain samples may be retained for a longer period, if necessary, to comply with applicable laws, regulations, or laboratory certification standards.

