- body fat-free mass (kg) measured by the difference between BW and body fat mass
- body fat mass (kg) measured using DXA
- Percentage of body fat mass measured using DXA

Secondary efficacy measure to assess the effect of study treatment on lipid metabolism:

- triglycerides, cholesterol, low-density lipoprotein (LDL), very low-density lipoprotein (VLDL), and HDL cholesterol, free fatty acid (FFA), glycerol, 3-hydroxybutyrate, and acylcarnitines assessed during sMMTT;
- apolipoprotein B-48 (ApoB-48), apolipoprotein B-100 (ApoB-100), apolipoprotein C-III (ApoC-III), and lipoprotein lipase (LPL) during sMMTT.
- leptin, adiponectin, insulin-like growth factor binding protein (IGFBP) 1 and 2 at fasting

Secondary efficacy measure to assess the effect of study treatment on insulin sensitivity:

- fasting insulin resistance as measured by the HOMA2 method (HOMA2-IR) (Hill et al. 2013) and postprandial insulin sensitivity indices (Matsuda [Matsuda and DeFronzo 1999], Oral Glucose Insulin Sensitivity [OGIS] Index [Mari et al. 2001], and Stumvoll Index [Stumvoll et al. 2000]); assessed during sMMTT (Hill et al. 2013);

Secondary efficacy measure to assess the effect of study treatment on glucose control:

- fasting and postmeal glucose (total and incremental area under the concentration versus time curve (AUC) from time zero to 240 minutes after start of the meal [ $\text{AUC}_{0-240\text{min}}$ ]) during sMMTT;
- hemoglobin A1c

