Administered 16 times: Day -3 (lead in), weekly from Week 1 through Week 15 (Day 1, Day 8, Day 15, Day 22, Day 29, Day 36, Day 43, Day 50, Day 57, Day 64, Day 71, Day 78, Day 85, Day 92, Day 99), and Week 18 (Day 123).

Lipid panel (Including triglycerides, total cholesterol, LDL-C, VLDL-C, HDL-C, ApoB-48, ApoB-100, ApoC-III, and LPL)

3-hydroxybutyrate (ie beta-hydroxybutyrate), acylcarnitines, FFA, and glycerol

Leptin, adiponectin, IGFBP 1 and IGFBP 2

Day -4 (lead in, 10 minutes prior to sMMTT [fasting]), Day 29 (Week 5; fasting), Day 57 (Week 9; fasting), Day 122 (Week 18; 10 minutes prior to sMMTT [fasting])

HbA1c

Screening, Day -4 (lead in), Day 57 (Week 9), and Day 122 (Week 18), safety follow-up visit

AUC Calculation

All area under the concentration versus time curve (AUC) measures will be calculated using the trapezoidal rule. For example, if $\{x_k\}$ is a partition of the desired time interval [a,b], where measurements at each x_k is denoted as y_k and $a = x_0 < x_1 < \cdots < x_{N-1} < x_N = b$.

• Total AUC (trapezoidal rule) is defined as

$$AUC_{[a,b]} = \sum_{k=1}^{N} \frac{(y_k + y_{k-1})(x_k - x_{k-1})}{2}$$

 Incremental AUC measures use the time zero value relative to the AUC measured unless otherwise specified, ie

incremental
$$AUC_{[a,b]} = AUC_{[a,b]} - y_0 \times (b-a)$$

Note:

- 1. If any lab measurements above are
 - a. below the quantification limit (eg <QL), $\frac{1}{2}$ × QL will be used instead for calculation;
 - b. above the quantification limit (eg >QL), 1.1 × QL will be used instead for calculation,

if deemed appropriate after review of data.

- 2. Unless otherwise specified, in case of no planned collection at 0 minute (fasting) for blood samples:
 - For pre-sMMTT serum glucose and serum insulin, the average of non-missing measurements at -1, -10 minutes will be used as the value for 0 minute to calculate AUC
 - For pre-sMMTT 3-hydroxybutyrate, acylcarnitines, FFA, and glycerol, lipid panel, the measurement at -10 minute will be used as the value for 0 minute to calculate AUC.
- 3. For $AUC_{[a,b]}$, if measurement of any timepoints between time a and b (ie a < t < b) is missing, then this timepoint will not be used in the calculation. AUC will be calculated based on non-missing measurement and timepoints. If measurements at time a and b are missing, then AUC will be missing.

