All the above lipid metabolism lab measurements will be calculated for (1) fasting; (2) total AUC_{0-4hr} ; (3) incremental AUC_{0-4hr} for analyses.

Note: For fasting measurements, it is collected on Day -4 (lead in, 10 minutes prior to sMMTT), Day 29 (Week 5), Day 57 (Week 9), Day 122 (Week 18; 10 minutes prior to sMMTT). For AUC parameters, it is derived for baseline and Week 18 during sMMTT.

Note: See Section 6.9.1 for AUC calculation details. All these fasting lab measurements and AUCs will be reported in both International System of Units (SI Units) and conventional units.

- change from baseline to Week 18 in lab measurements during sMMTT of:
 - o ApoB-48
 - o ApoB-100
 - o ApoC-III
 - o LPL

All the above lipid metabolism lab measurements will be calculated for (1) fasting; (2) total AUC_{0-4hr}; (3) incremental AUC_{0-4hr} for analyses.

Note: For fasting measurements, it is collected Day -4 (lead in, 10 minutes prior to sMMTT), Day 29 (Week 5), Day 57 (Week 9), Day 122 (Week 18; 10 minutes prior to sMMTT). For AUC parameters, it is derived for baseline and Week 18 during sMMTT.

Note: See Section 6.9.1 for AUC calculation details. All these fasting lab measurements and AUCs will be reported in both SI Units and conventional units.

The above available laboratory fasting parameters will be analyzed in a manner similar to the secondary PD analysis on body weight using MMRM to compare the effect of tirzepatide versus placebo.

- ➤ Independent variables: treatment, time, and treatment-by-time interaction as fixed effects, baseline as a covariate, and patient as a random effect
- Response variable: change from baseline

The above available laboratory AUC parameters during sMMTT will be analyzed using ANCOVA to compare the effect of tirzepatide versus placebo:

- ➤ Independent variables: treatment as a factor, baseline as a covariate
- Response variable: change from baseline to Week 18.

Time profile plots of the lab measurements (mean \pm standard deviation) during sMMTT (over 6 time points) will be provided by treatment for baseline and Week 18.

- change from baseline through Week 18 in fasting concentration of:
 - o leptin
 - o adiponectin
 - o IGFBP 1
 - o IGFBP 2

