The above fasting leptin, adiponectin, IGFBP 1 and 2 will be analyzed in a manner similar to the secondary PD analysis on body weight using MMRM since the lab tests are scheduled to be measured at baseline (Day -4) and 3 times postbaseline (Day 29 [Week 5], Day 57 [Week 9] and Day 122 [Week18]).

- ➤ Independent variables: treatment, time, and treatment-by-time interaction as fixed effects, baseline as a covariate, and patient as a random effect
- Response variable: change from baseline

Note: If any lab measurements above are (1) below the quantification limit (eg <QL), $\frac{1}{2} \times$ QL will be used instead for calculation; (2) above the quantification limit (eg >QL), $1.1 \times$ QL will be used instead for calculation, if deemed appropriate after review of data. All these lab fasting measurements will be reported in both SI Units and conventional units.

Insulin Sensitivity

Secondary PD measures to assess the effect of tirzepatide 15 mg versus placebo on insulin sensitivity:

- change from baseline to Week 18 in insulin sensitivity indices assessed during sMMTT:
 - o **HOMA2-IR** (insulin resistance as measured by the HOMA2 method using fasting glucose [mmol/L] and fasting insulin [pmol/L] for calculation) (Hill et al. 2013)
 - Fasting measurement of glucose and insulin will be the mean of non-missing measurements at -10 and -1 minutes of sMMTT
 - Serum glucose and serum insulin are collected during sMMTT and used for calculation of HOMA2-IR and indices below.
 - If glucose or insulin values are outside of ranges of inputs in HOMA2-IR lookup table, HOMA2-IR will be missing.

Matsuda Index (postprandial insulin sensitivity from sMMTT) (Schlichtkrull et al. 1965; Matsuda and DeFronzo 1999; Service and O'Brien 2001)

$$ISI-Matsuda = \frac{10,000}{\sqrt{G_0*I_0*\frac{total\ glucose\ AUC_{0-4hr}}{4hr}*\frac{total\ insulin\ AUC_{0-4hr}}{4hr}}}$$

where G_0 and I_0 are the glucose concentration (mg/dL) and insulin concentration (μ U/mL) at 0 minute (fasting).

Note: Fasting measurement will be the mean of non-missing measurements at -10 and -1 minutes of sMMTT.

o OGIS Index (Oral Glucose Insulin Sensitivity Index) (Mari et al. 2001)

$$OGIS = \frac{1}{2} \times \left(B + \sqrt{B^2 + 4p_5p_6(G_{120min} - G_{CLAMP})Cl_{OGTT}} \right)$$

Where

$$B = [p_5(G_{120min} - G_{CLAMP}) + 1] \times Cl_{OGTT}$$

$$Cl_{OGTT} = p4 \frac{p_1D_0 - V(G_{180min} - G_{120min})/60min}{G_{120min}} + \frac{p_3}{G_0}$$

$$I_{120min} - I_0 + p_2$$

Where

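### The SAP voids an AUC only when both end-point samples are missing, so a lost 240-minute sample can leave a truncated sum reported as the 0–4 hour AUC

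*SAP*

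**What the plan says.** SAP 6.9.1 (AUC Calculation) defines the AUC by the trapezoidal rule on a partition of [a, b] whose first point is a and last point is b. The incremental AUC is the total minus y0 × (b − a).

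Note 3 handles missing samples in three steps:

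- Where "any timepoints between time a and b (ie a < t < b) is missing", the point is left out.
- The AUC is calculated from whatever measurements and times are not missing. This sentence is not itself restricted to interior points.
- "If measurements at time a and b are missing, then AUC will be missing".

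Note 2 deals with the absence of a planned sample at minute 0. Glucose and insulin use the mean of the available −10 and −1 minute values. For lipids and metabolites, "the measurement at -10 minute will be used as the value for 0 minute to calculate AUC". No note supplies a value at 240 minutes.

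The interval is fixed elsewhere. Protocol 9.1.2 defines the glucose AUC "from time zero to 240 minutes after start of the meal", and SAP 6.9.2.2 labels the lipid and glucose AUCs as 0–4 hr. For the lipid measures, "For AUC parameters, it is derived for baseline and Week 18 during sMMTT". The "Matsuda Index (postprandial insulin sensitivity from sMMTT") divides total glucose AUC and total insulin AUC by a fixed 4 hours each.

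**The concern.** One lost end point is the case that needs a rule, and Note 3 does not give it one. Taken literally, its last sentence acts only when both ends are missing. With only the 240-minute sample lost, the middle sentence allows a calculation on the remaining points. The result covers 0–180 or 0–210 minutes but is reported and analysed as 0–4 hours.

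The error has a known direction for each affected profile. Total and incremental AUC come out too low at that visit. The change from baseline is therefore too low if Week 18 is affected and too high if baseline is affected; a wrong baseline also enters the ANCOVA as the covariate. Matsuda errs upward, because the truncated totals sit in its denominator.

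Exposed are the total and incremental AUCs of 13 lipid and metabolite measures (nine in the first list in SAP 6.9.2.2, Lipid Metabolism, four in the second), the glucose AUCs, and Matsuda. SMR, the fasting values, HOMA2-IR, OGIS and Stumvoll use no AUC.

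**Working it through.** The plan gives no figure to reproduce here. The check applies the SAP formulas to the SAP sampling times.

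**Inputs (SAP 6.9.1).** Post-meal samples:

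- Glucose: 15, 30, 60, 90, 120, 150, 180, 210, 240 min
- Insulin: 15, 30, 60, 90, 120, 180, 240 min
- Lipids and metabolites: 60, 90, 120, 180, 240 min

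The last interval is therefore 30 of 240 minutes for glucose and 60 of 240 for the others. Time 0 comes from Note 2.

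**Flat profile at level y0, 240-minute sample lost**

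| | True total | Computed total | Error | Computed incremental (true value 0) |
|---|---|---|---|---|
| Lipids, metabolites | 240·y0 | 180·y0 | −25% | 180·y0 − 240·y0 = −60·y0 |
| Glucose | 240·y0 | 210·y0 | −12.5% | 210·y0 − 240·y0 = −30·y0 |
| Insulin (enters Matsuda) | 240·y0 | 180·y0 | −25% | not used |

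**Sign of the incremental AUC, any profile.** The truncated total is the mean level over the covered time multiplied by that time. After subtracting 240·y0 the result is negative unless the mean level exceeds:

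- Lipids and metabolites: 240/180 = 133% of fasting over 0–180 min
- Glucose: 240/210 = 114% of fasting over 0–210 min

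**Matsuda, flat profiles.** The index is proportional to 1/√(glucose AUC × insulin AUC), each over a fixed 4 hours. No baseline is subtracted.

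- Glucose sample lost: 1/√0.875 = 1.069 (+6.9%)
- Insulin sample lost: 1/√0.75 = 1.155 (+15.5%)
- Both lost: 1/√(0.875 × 0.75) = 1.234 (+23.4%)

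**Illustrative triglyceride profile (assumed, not from the documents).** Values 150, 165, 175, 182, 190, 185 mg/dL at 0, 60, 90, 120, 180, 240 min.

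- Trapezoids: 9,450 + 5,100 + 5,355 + 11,160 + 11,250 = 42,315
- Without 180 min: the last two become (182 + 185)/2 × 120 = 22,020, total 41,925
- Without 240 min: 42,315 − 11,250 = 31,065
- Fasting rectangle: 150 × 240 = 36,000

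| | Total | Incremental |
|---|---|---|
| Complete | 42,315 | +6,315 |
| 180 min lost (interior) | 41,925 | +5,925 (−6%) |
| 240 min lost | 31,065 | −4,935 |

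The interior rule does little harm. Truncation at the end reverses the sign. The mean over 0–180 min is 31,065/180 = 172.6, which is 115% of fasting and below the 133% threshold.

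**Start of the interval.** Lipids and metabolites have a single pre-meal sample. If it is lost and the sum starts at 60 min, a flat total is 180·y0 against 240·y0, or 25% low. There y0 is absent too, so no incremental AUC can be formed; only the total is at issue. Glucose and insulin lose their start only if both pre-meal samples are lost.

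**Scale in one arm (illustration).** About 46 completers gives 23 per arm. If every subject in an arm had the profile above, one lost Week 18 end-point sample would move that arm's mean incremental AUC by 11,250/23 = 489 mg·min/dL, about 8% of 6,315.

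**The case against.** **The SAP's own definition points to either end.** The partition ends at b, the skip rule is limited to points strictly inside the interval, and the endpoints are named 0–4 hr. Without the value at b that AUC is undefined, and the sentence can be read in ordinary English as meaning either end. This has real force as evidence of intent. It does not settle the text: the middle sentence is not limited to interior points, and two programmers could derive different datasets from the same note.

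**The sign reversal needs a mismatch.** Someone who ends the sum at 180 minutes could also subtract y0 × 180, and a flat profile then gives zero. But the endpoint sets b at 4 hours, the incremental formula uses b − a, and Matsuda's 4-hour divisor is written out. A matched width would also not give the planned quantity: in the example it is 31,065 − 27,000 = 4,065 against 6,315, and the total is still truncated.

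**Frequency is unknown.** This stands. A cannula is placed for serial sampling (protocol Appendix 6, Section 6.9), and nothing suggests that losses would differ by arm. The protocol does foresee failures or delays in obtaining samples "due to legitimate clinical issues (eg, equipment technical problems, venous access difficulty", though as a general statement covering all procedures.

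**Setting to missing is not the only remedy.** Also true. Carrying the last value to 240 minutes changed the total by about 0.1% (glucose), 3.1% (insulin) and 0.7% (triglycerides) on a separate set of assumed curves. That would be a new imputation rule, whereas the one-word change fits the definition already in the SAP.

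**Conclusion.** The concern holds. As written, Note 3 does not void an AUC when one end point is missing, and followed literally it yields a wrong value for that subject and visit. On a flat profile the total is 25% low (lipids, metabolites, insulin) or 12.5% low (glucose), and Matsuda is up to 23.4% high; the incremental AUC can change sign.

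These sizes are per affected profile and assume the literal reading. The incremental figures also assume the full 240-minute width that the formula prescribes. No directional bias in the treatment comparison is shown, because neither the loss rate nor its split by arm is known. The SAP authors may well have meant either end point. With only secondary endpoints exposed, this should be corrected, but it does not threaten the primary analysis.

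**What to change.** In the last sentence of SAP 6.9.1, AUC Calculation, Note 3, replace *and* with *or*, so that it reads: *If the measurement at time a or at time b is missing, then AUC will be missing.* Time a should be understood as the value supplied by Note 2, so one available pre-meal sample still suffices for glucose and insulin. Leave the interior-point rule unchanged.

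The cost is one word and a matching programming check before database lock. A few AUCs, and the Matsuda values that depend on them, become missing instead of being computed on a shortened interval. SAP 6.2 requires a protocol amendment only when a principal feature changes, so this can be documented in the SAP.

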6.9.2. Pharmacodynamic Statistical Inference

Unless specified otherwise, PD parameters at baseline and post baselines, as well as change from baseline values, will be summarized by treatment, and the change from baseline to Week 18 will be analyzed.

6.9.2.1. Primary Pharmacodynamic Analyses Sleep Metabolic Rate

The primary endpoint in the study is the change from baseline (Day -3 to -1) to Week 18 (Day 123 to 125) in sleep metabolic rate (SMR; energy expenditure during sleep period) for comparison of tirzepatide 15 mg versus placebo, which is measured in the respiratory chamber (whole-room calorimetry).

The primary endpoint will be analyzed using analysis of covariance (ANCOVA) to compare the effect of tirzepatide versus placebo at Week 18 on SMR (kcal/day):

- ➤ Independent variables: treatment as a factor, baseline SMR (kcal/day), change from baseline to Week 18 in fat free mass, and change from baseline in fat mass as covariates.
- Response variable: change from baseline to Week 18 in SMR.
- ➤ Where Fat Mass = DXA Region Fat (%)/100 * DXA Weight
- ➤ Where Fat Free Mass = DXA Weight Fat Mass.

Baseline SMR will be analyzed with analysis of variance (ANOVA) with independent variable, treatment as a factor.

Note: Energy expenditure is calculated for sleep period and extrapolated to 24 hours. The calculated sleep metabolic rate (sleep EE in Event Data) will be provided in datasets to statisticians/programmers. The average value of nonmissing measurements at Days -3, Day -2 (two 23-hr sessions) will be used as value for baseline, and the average value of nonmissing measurements at Days 123, Day 124 will be used as value for Week 18.

Inferential statistics include least squares (LS) means and standard error of SMR for tirzepatide versus placebo, the estimated treatment difference (tirzepatide - placebo), and corresponding 2-sided 95% CI, and associated p-value.

Sensitivity analysis on primary endpoint will be conducted in a similar manner on the body weight target population (ie subjects who reach the body weight target range of $-10\% \pm 2\%$ [-8% to -12%, inclusive] at Week 18 from baseline and have evaluable PD data).

Additional analyses will be conducted with ANCOVA with

- Independent variables: treatment as a factor, baseline SMR (kcal/day), change from baseline to Week 18 in DXA weight as covariates
- Response variable: change from baseline to Week 18 in SMR

Additional analyses may be conducted as follows:

- Step 1: conduct ANCOVA model with
 - o Independent variables: baseline fat free mass, baseline fat mass, age, sex
 - o Response variable: baseline SMR
 - Where Fat Mass = DXA Region Fat (%)/100 * DXA Weight
 - Where Fat Free Mass = DXA Weight Fat Mass.
- Step 2: with estimated model from Step 1 to predict SMR at Week 18 using
 - Week 18 fat free mass, Week 18 fat mass, age, sex
- Step 3: calculate:
 - magnitude of residual SMR at Week 18 (metabolic adaptation)
 - = SMR measured at Week 18 SMR predicted at Week 18 from Step 2
- Step 4: conduct ANOVA on metabolic adaptation at Week 18 from Step 3 to compare tirzepatide to placebo

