5.2. Determination of Sample Size

[figure not shown]
Up to 56 subjects are planned to be randomized so that approximately 46 subjects complete the study assuming 15% discontinuation rate. These 56 subjects will be randomized to QW tirzepatide or placebo in a 1:1 ratio. The estimated standard deviation of the change in SMR from baseline is 117 kcal/day (Heilbronn et al. 2006). With an expected treatment difference of 100 kcal/day, this provides at least 80% power for the comparison of tirzepatide versus placebo based on 2 sample t-test using 2-sided test at alpha level of 0.05 for the assessment of the primary endpoint.

Abbreviations: DXA = dual energy X-ray absorptiometry; FCI = Food Craving Inventory; FPQ = Food Preference Questionnaire; QW = once weekly; sMMTT = standardized mixed-meal tolerance test; VAS = visual analog scale.

Figure GPGU.5.1. Illustration of study design for Protocol I8F-MC-GPGU.

Clinical Research Unit Procedures

Abbreviations: DXA = dual energy X-ray absorptiometry; FCI = Food Craving Inventory; FPQ = Food Preference Questionnaire; sMMTT = standardized mixed-meal tolerance test; VAS = visual analog scale.

Figure GPGU.5.2. Illustration of clinical research unit procedures.

6. A Priori Statistical Methods

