- protein
 - og

- o kcal
- o percent of energy (protein [kcal]/energy intake [kcal])
- fat (saturated and unsaturated)
 - o g
 - kcal
 - o percent of energy (fat [kcal]/energy intake [kcal])

Note: Food intake will be quantified separately for lunch, dinner, and combined for lunch and dinner. The amount of grams of fat, carbohydrates and protein consumed during lunch and during dinner will be documented in eCRF. There are 4 kcal in a gram of carbohydrate or protein, and 9 kcal in a gram of fat will be used to calculate energy intake related variables.

The above food intake parameters (at lunch, at dinner, and at lunch and dinner combined) will be analyzed using ANCOVA to compare the effect of tirzepatide versus placebo:

- ➤ Independent variables: treatment as a factor, baseline as a covariate
- Response variable: change from baseline to Week 18

Energy Expenditure (EE)

Secondary PD measures to assess the effect of tirzepatide 15 mg versus placebo on parameters of EE:

• change from baseline to Week 18 in 24-hour EE

The baseline 24-hr EE will be analyzed with ANOVA with independent variable, treatment as a factor.

At Week 18, the 24-hour EE will be analyzed with 2 ANCOVA models (similar to primary endpoint SMR)

- ➤ Model 1:
 - Independent variables: treatment as a factor, baseline 24-hr EE (kcal/day), change from baseline to Week 18 in fat free mass, and change from baseline in fat mass as covariates.
 - Response variable: change from baseline to Week 18 in 24-hr EE.
 - Where Fat Mass = DXA Region Fat (%)/100 * DXA Weight
 - Where Fat Free Mass = DXA Weight Fat Mass.
- ➤ Model 2 (additional analyses):
 - o Independent variables: treatment as a factor, baseline 24-hr EE (kcal/day), change from baseline to Week 18 in DXA weight as covariates
 - o Response variable: change from baseline to Week in 24-hr EE

Additional analyses may be conducted as follow:

- Step 1: conduct ANCOVA model with
 - o Independent variables: baseline fat free mass, baseline fat mass, age, sex
 - o Response variable: baseline 24-hr EE
 - Where Fat Mass = DXA Region Fat (%)/100 * DXA Weight

- Where Fat Free Mass = DXA Weight Fat Mass.
- Step 2: with estimated model from Step 1 to predict 24-hr EE at Week 18 using
 - Week 18 fat free mass, Week 18 fat mass, age, sex
- Step 3: calculate:
 - magnitude of residual 24hr EE at Week 18
 - = 24hr EE measured at Week 18 24hr EE predicted at Week 18 from Step 2

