- Step 4: conduct ANOVA on residual 24-hr EE at Week 18 from Step 3 to compare tirzepatide to placebo

Substrate Oxidation Rate

Secondary PD measures to assess the effect of tirzepatide 15 mg versus placebo on parameters of substrate oxidation rates:

Respiratory quotient

- change from baseline to Week 18 in 24-hour respiratory quotient (RQ; ratio)
- change from baseline to Week 18 in sleep RQ (ratio)
- change from baseline to Week 18 in duration of periods with RQ<0.80 (minute)

The above RQ parameters will be analyzed with ANCOVA model

- ➤ Independent variables: treatment as a factor, baseline RQ parameter value as a covariate
- ➤ Response variable: change from baseline to Week 18 in RQ parameter

Protein, fat, carbohydrate oxidation

- change from baseline to Week 18 in protein oxidation (g/day)
- change from baseline to Week 18 in fat oxidation (g/day)
- change from baseline to Week 18 in carbohydrate oxidation (g/day)

The above oxidation rates parameters will be analyzed with

- Step 1: calculate adjusted oxidation parameters Adjusted oxidation rate (g/day) = oxidation rate (g/day) / 24-hr EE (kcal/day) * 1000 (kcal/day)
- ➤ Step 2: ANCOVA model
 - Independent variables: treatment as a factor, baseline adjusted oxidation rate as a covariate
 - Response variable: change from baseline to Week 18 in adjusted oxidation rate parameters

Note: 24-hr energy expenditure, RQ, protein oxidation, fat oxidation, and carbohydrate oxidation are calculated based on 23-hour measurement period and extrapolated to 24 hours. RQ will also be calculated for sleep period and extrapolated to 24 hours. The calculated 24-hr EE, 24 hr RQ, sleep RQ (in Event Data), duration of period with RQ<0.8, and 24-hr substrate oxidation (protein, fat, carbohydrate oxidation) will be provided in datasets to statisticians/programmers.

The average value of nonmissing measurements at Days -3, Day -2 (two 23-hr sessions) will be used as value for baseline, and the average value of nonmissing measurements during Days 123, Day 124 will be used as value for Week 18.

Body Weight and Body Composition

Secondary PD measures to assess the effect of tirzepatide 15 mg versus placebo on parameters of body weight, and body composition using DXA scan:

- change from baseline to Week 18 in
 - o body weight (scale weight; kg)

Note: Body weight is measured twice at each visit, and the average of non-missing measurements will be used for analyses.

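### The optional metabolic-adaptation comparison is a treatment-only ANOVA and leaves out the baseline residual, which costs precision unless the residual correlation is low

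*SAP*

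**What the plan says.** SAP 6.9.2.1 (Primary Pharmacodynamic Analyses, SMR) closes with a four-step analysis that "may be conducted as follows":

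- **Step 1** models baseline SMR with "Independent variables: baseline fat free mass, baseline fat mass, age, sex".
- **Step 2** applies that fit to Week 18 fat-free mass and fat mass, with age and sex.
- **Step 3** defines metabolic adaptation as measured SMR at Week 18 minus "SMR predicted at Week 18 from Step 2".
- **Step 4** is to "conduct ANOVA on metabolic adaptation at Week 18 from Step 3 to compare tirzepatide to placebo".

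Step 4 names no covariate. Where the same section uses ANOVA for baseline SMR, it gives treatment as the independent variable, so Step 4 is naturally read as treatment only.

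SAP 6.9.2.2 (Energy Expenditure) has the same four steps for 24-hour EE, also optional ("Additional analyses may be conducted as follow"), ending with "conduct ANOVA on residual 24-hr EE at Week 18 from Step 3 to compare tirzepatide to placebo".

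The primary model in SAP 6.9.2.1 is different. It is an ANCOVA of change in SMR with treatment, baseline SMR, and the changes in fat-free mass and fat mass.

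**The concern.** Two people with the same body composition, age and sex can differ persistently in SMR. That offset shows up as a residual at baseline and, to the extent that it is stable, again at Week 18. Step 4 analyses the Week 18 residual alone, so the offset counts as between-subject noise, although Step 1 has already measured it before treatment.

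The choice is also out of line with the rest of the plan. The other between-arm models of post-baseline PD measures in SAP 6.9.2 adjust for baseline, and Protocol 10.3.3.2 sets that default for PD parameters measured once after baseline. This is not a contradiction: the analysis is optional, and SAP 6.9.2 allows exceptions. But the SAP gives no reason for this one.

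Reduced metabolic adaptation is part of the hypothesis in Protocol 3.2, and this is the only analysis that the SAP labels with that term. If it is run and the residuals are at least moderately correlated, its confidence interval will be wider than the collected data allow.

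**Working it through.** **Inputs.** SAP 5.2 gives about 46 completers randomized 1:1 (23 per arm), a two-sided alpha of 0.05 and an expected difference of 100 kcal/day. It also states: "The estimated standard deviation of the change in SMR from baseline is 117 kcal/day". That SD is for change in SMR, not for a residual. Neither document gives rho, the correlation between baseline and Week 18 residuals, so a range is used.

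**The plan's own figure.** For the primary comparison, SE = 117 × √(2/23) = 34.5. With a difference of 100 and 44 df, the noncentral t gives 80.9% power, which reproduces the stated minimum of 80%. The documents give no power or precision figure for the metabolic-adaptation analysis.

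**Relative precision.** The SE of the arm difference from ANCOVA on the baseline residual, relative to treatment-only ANOVA, is

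ratio = √[(1 − rho²) × (1 + 1/(46 − 4))].

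The second factor is the price of estimating the covariate slope. No SD is needed. The number per arm that ANOVA would need to match the ANCOVA is 23/ratio².

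| rho | SE ratio | ANOVA n per arm to match |
|---|---|---|
| 0 | √(1 × 1.0238) = 1.012 | – |
| 0.3 | √(0.91 × 1.0238) = 0.965 | 24.7 |
| 0.5 | √(0.75 × 1.0238) = 0.876 | 30.0 |
| 0.7 | √(0.51 × 1.0238) = 0.723 | 44.0 |

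The SEs are equal when (1 − rho²) × 43/42 = 1, so rho = √(1/43) = 0.152. On confidence-interval width, with 43 against 44 df, break-even is 0.157. Below that, plain ANOVA is slightly more precise.

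**Illustrative power** for an assumed 100 kcal/day difference, by noncentral t with 44 and 43 df. An SD must be assumed, and two readings of 117 are shown:

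- (a) 117 is the SD of the change in residual. With equal variances at the two visits, the Week 18 residual SD is 117/√(2(1 − rho)).
- (b) 117 is the Week 18 residual SD itself.

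| rho | (a) Week 18 SD | (a) SE, ANOVA v ANCOVA | (a) power | (b) SE, ANOVA v ANCOVA | (b) power |
|---|---|---|---|---|---|
| 0 | 82.7 | 24.4 v 24.7 | 98.0 v 97.7% | 34.5 v 34.9 | 81 v 80% |
| 0.3 | 98.9 | 29.2 v 28.1 | 92 v 93.5% | 34.5 v 33.3 | 81 v 83.5% |
| 0.5 | 117 | 34.5 v 30.2 | 81 v 90% | 34.5 v 30.2 | 81 v 90% |
| 0.7 | 151 | 44.5 v 32.2 | 59 v 86% | 34.5 v 24.9 | 81 v 97.5% |

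**Simulation check.** The formula ignores the fact that the Step 1 coefficients are themselves estimated. Steps 1 to 4 were therefore simulated in full, with 46 subjects, assumed body-composition values and weight loss, residual SD 117 at both visits, and 6,000 runs per rho under no effect.

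| rho | Empirical SE, ANOVA v ANCOVA | Ratio |
|---|---|---|
| 0 | 37.3 v 37.7 | 1.01 |
| 0.3 | 35.3 v 34.4 | 0.98 |
| 0.5 | 34.6 v 30.8 | 0.89 |
| 0.7 | 33.7 v 25.0 | 0.74 |

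Bias was within 1 kcal/day for both methods, and type I error lay between 4.5% and 6.0%. With a 100 kcal/day effect (3,000 runs per rho), rejection rates were 80 v 81% at rho 0.3, 80 v 88% at 0.5 and 82 v 97% at 0.7.

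The SE ratios apply equally to 24-hour EE. No power is given there because the documents state neither an SD nor a planning difference for it.

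**The case against.** The strongest reply is that nothing here is wrong. Step 4 is a valid comparison within an optional analysis that has no power claim and no decision attached. The main question is already answered with baseline adjustment: the primary ANCOVA compares SMR change given baseline SMR and the changes in fat-free and fat mass, which is substantially the same question. A further ANCOVA on DXA weight change is also planned, and the main 24-hour EE models adjust for baseline too. Protocol 10.3 would allow an adjusted version as an extra exploratory analysis. All of this stands, and it keeps the point minor. It does not remove the case for naming the covariate in advance, which avoids a later choice between adjusted and unadjusted results.

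The second reply is that the gain depends on a correlation the documents do not give. That also stands: at rho 0.3 the gain is only 2 to 3% of the SE. Two facts make a value near zero less plausible without proving it. Protocol 5.4 chose SMR for its reproducibility, and SAP 6.9.2.1 averages the available sessions of two 23-hour stays at each visit.

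The third reply concerns the power figures. The 59 v 86% contrast arises because fixing the SD of change at 117 forces the Week 18 residual SD up to 151, which no passage supports. That is fair: the powers are illustrations, and the SE ratios carry the argument. The formula also flatters the gain slightly; the simulated ratios at rho 0.3 to 0.7 are about 0.01 to 0.02 higher.

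**Conclusion.** The point holds, at low importance. If the optional analysis is run as written, for SMR or for 24-hour EE, it discards a baseline covariate that Step 1 already produces. The cost is precision only, and the primary analysis is unaffected.

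With 46 completers, adjustment would leave the SE about 1% wider at rho 0, 2 to 3% narrower at 0.3, 11 to 12% narrower at 0.5 and 26 to 28% narrower at 0.7 (simulation and formula respectively). The gain is thus small, moderate or large depending on rho. These ratios rest on the assumed rho and on 23 completers per arm. The power figures also assume a residual SD and a 100 kcal/day difference, neither of which the documents state for a residual.

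**What to change.** In Step 4 of SAP 6.9.2.1 (SMR) and of the Energy Expenditure part of SAP 6.9.2.2 (24-hour EE), replace the ANOVA with:

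> ANCOVA of the Week 18 residual from Step 3, with treatment as a factor and the subject's baseline residual (measured minus predicted baseline value from Step 1) as a covariate.

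Use the baseline residual as a covariate and do not simply subtract it. With equal variances, the change in residual has 2(1 − rho) times the ANOVA variance, so below rho 0.5 it is less precise than the present plan.

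The cost is one sentence in two places, one degree of freedom, and about 1% on the SE if rho is near zero. No new data are needed.
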